5. STUDY DESIGN

5.1. Overall Design

Participants will be screened to randomize approximately 172 participants into 2 groups, an EN3835 group (n ~86) and a placebo group (n ~86) in a 1:1 ratio. Study intervention will be administered intralesionally to all nodules present based on the size of each nodule at the doses described in the dosage table (Table 2). All nodules present on each foot on Day 1 must be treated. (If all nodules on each foot are not hard, firm throughout, moderately firm on Screening and Day 1, the participant will not be eligible for study inclusion). Nodules will be measured using calipers and the largest width or length will be used to determine the number of injections to be administered in each nodule. The total number of study intervention injections across all nodules present, shall not exceed 3 injections (1.35 mg) in a single foot when treating participants with unilateral plantar fibromatosis. When treating participants with bilateral plantar fibromatosis, the total number of study intervention injections across all nodules present shall not exceed 4 injections (1.8 mg) in total with each foot receiving a maximum dose of 0.9 mg. After receiving study intervention, participants will be encouraged to resume normal daily activities including walking and bearing weight on the treated foot/feet. All participants will return to the clinic for 4 follow-up visits, 2 weeks apart, on Days 15, 29, 43, and 57.

At the Day 29 visit, if the participant has any previously treated nodule(s) that remains palpable and measurable by caliper with a consistency of hard, firm throughout, moderately firm, or soft that is/are deemed appropriate for treatment by the investigator, and the Treatment 2 Criteria are met, a second dose of the study intervention may be administered.

For all participants, at the time points listed in the Schedule of Assessments, the efficacy of the study intervention will be assessed on the FFI (adapted for plantar fibromatosis; May 2021), the Subject Satisfaction with Treatment Scale, the PGIC PF Overall and individual PGIC subscales of pain, difficulty, and activity limitation, the Pain Intensity NRS, the PGIS PF Overall, and the individual PGIS subscales of pain, difficulty, and activity limitation, and the Clinician Global Impression of Change Scale. Safety will be assessed by evaluating the incidence and duration of TEAEs, AESIs, SAEs, and changes in vital signs and clinical laboratory values.

All participants will complete the study on EOS (Day 57) Visit, regardless of whether they receive 1 or 2 treatments during the study. At the EOS visit, immunogenicity samples will be collected, safety will be assessed, and nodules will be measured. The maximum duration of participation is up to 85 days (Screening Period: 28 days, Treatment Periods: 1 or 2 days, and a total Follow-up Period of 56 days).

5.2. Scientific Rationale for the Study Design

Study EN3835-105 is a completed, open-label study conducted to assess the safety, tolerability, and PK of EN3835 in the treatment of plantar fibromatosis. The effect of EN3835 on nodule size was assessed and a validated assessment tool (ie, Foot Function Index-Short Form-23 [FFI-SF-23]) was used to obtain a preliminary assessment of the treatment with EN3835 on multiple functional domains (eg, foot pain, disability, and difficulty) considered representative of clinically meaningful endpoints in the treatment of plantar fibromatosis. Results of an interim analysis from this study showed that participants receiving EN3835 showed improvement in the

severity of their plantar fibromatosis symptoms of pain, difficulty, and disability (activity limitation) with improvements more prominent with the 1.2 mg/mL or 2.25 mg/mL doses. Both participants and investigators saw an improvement in nodule consistency by Day 57. All AEs in this study were considered mild to moderate in severity and most were TEAEs related to the injection site. Most AEs resolved within 21 days.

Study EN3835-222 is a randomized, double-blind, placebo-controlled study will evaluate the efficacy and safety of up to 2 doses of EN3835 vs placebo in participants with plantar fibromatosis. Participants will receive a maximum dose of up to 1.8 mg per treatment for up to 2 treatments based on the configuration of their nodules. For participants with bilateral plantar fibromatosis, no more than 2 injections (0.9 mg) per foot can be administered. For participants with unilateral plantar fibromatosis, no more than 3 injections (1.35 mg) may be administered in the single foot. Multiple nodules may be treated on the same foot.

Efficacy and safety data will be collected throughout the study.

5.2.1. Changes in the Study Design Due to COVID-19

The COVID-19 public health emergency has disrupted the conduct of clinical research throughout the world. At Endo, ensuring the safety of clinical study participants is our primary concern. In addition, the integrity of data obtained from clinical studies must be ensured.

To ensure participant safety and protect data integrity with Endo's approval, Endo may allow remote visits for certain safety assessments. This is aligned with the FDA Guidance on *Conduct of Clinical Trials of Medical Products During the COVID-19 Public Health Emergency* (March 2020, updated 30 August 2021).

Additionally, participants impacted by the health emergency will be allowed to continue in the study and complete assessments when the investigational sites re-open as follows:

- A participant who had received any dose of EN3835 in the study prior to an interruption will be allowed to continue in the study.

5.2.2. Justification for Dose

EN3835-105 was a randomized dose-ranging study during which in the initial phase, the safety and effectiveness of 3 different concentrations of EN3835: 0.6, 1.2, and 2.25 mg/mL, were studied. In addition, nodules which were 1.5 cm or smaller in diameter received 1 injection while nodules that exceeded 1.5 cm received 2 injections. Once all participants completed the initial study phase, an interim analysis was done to compare the 3 concentrations and select the optimal concentrations for use in the retreatment phase of EN3835-105 and EN3835-222 overall.

In EN3835-105, at the time of the interim analysis, there were an insufficient number of participants with at least a 50% score on the pain subscale to evaluate the 2.25 mg/mL cohort treatment effect. To evaluate this population participants who had a baseline total FFI-SF-23 score of at least 34 were selected to evaluate the treatment effect.

The following criteria were to be collected throughout the study and used to evaluate the dose selection: safety (incidence and severity of AEs), nodular consistency, nodule size (area), and FFI-SF-23 response in subdomains of Pain, Difficulty, and Disability.

Safety data along with a combination of observed change in nodule characteristics (size and consistency) in addition to participant-reported responses to the FFI-SF-23 were used to evaluate the response to 0.6, 1.2, and 2.25 mg/mL of EN3835.

The combination of responses to each of the 3 categories were assigned levels of treatment response (Very good, Good, Some, No, and Poor) as below:

Very good treatment response was defined as a non-palpable nodule (no measurable size or consistency) and reduction in FFI-SF-23 score.

Good treatment response was defined as a reduction in all 3 categories.

Some treatment response was defined as a reduction in 2 of the 3 categories.

No treatment response was defined as a reduction in 1 category and no change in the other 2.

Poor treatment response was defined as no reduction in any category.

Worsening (significant increase in size, increase in hardness or increase in composite FFI-SF-23 response) in any category was considered a Poor treatment response.

At the time of the interim analysis of EN3835-105 there were 24 total treatment-related AEs in the 0.6 mg/mL group, 16 treatment-related AEs in the 1.2 mg/mL group, and 15 treatment-related AEs in the 2.25 mg/mL group. All AEs were of mild to moderate intensity and most resolved within 21 days. The safety profiles, including the type (injection site reactions, including pain, bruising, swelling, and ecchymosis), intensity, and duration of the treatment related AEs were similar among treatment groups. It was concluded that all concentrations were equally safe and well tolerated.

Dose Selection

Rodent studies assessed the effects of intravenous injection of EN3835 directly into the systemic circulation. Dose-dependent liver toxicity was noted at exposures greater than or equal to 13 times the 2.7 mg of the maximum recommended human dose on a mg/kg basis (Study LAB 1007-1671). Since the proposed maximum total dose of EN3835 recommended for intralesional injection per treatment visit will be much lower than the intravenous injection administered in rodent studies, Endo considers the proposed dose will have no risk of systemic toxicity.

Based on the aforementioned data, it was concluded that in the interim analysis of Study EN3835-105, both the 1.2 and 2.25 mg/mL concentrations had a better treatment effect versus the lowest concentration, 0.6 mg/mL. Participants who received 2 injections of either 1.2 mg/mL or 2.25 mg/mL had a better treatment effect compared to those receiving 1 injection. A better treatment response on the FFI was observed in participants who received 2 injections of 2.25 mg/mL compared to those receiving 2 injections of 1.2 mg/mL. Overall, participants in the 2.25 mg/mL group had the best treatment responses as defined above. Paired with the nearly equivalent safety profile between the 2 concentrations, the 2.25 mg/mL concentration was selected to be used in the retreatment phase of Studies EN3835-105 and EN3835-222. The maximum total dose of EN3835 to be administered during this study when both feet are treated is 1.8 mg, and the maximum dose administered to a single foot is 1.35 mg when only 1 foot is treated, given that these were the maximum doses evaluated in Study EN3835-105.

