3.2.1. EN3835-105 (Proof of Concept)

Study EN3835-105 is a completed Phase 1, open-label, randomized, dose-ranging proof of concept study. The safety, immunogenicity, PK, and effect of EN3835 on nodule size in 24 participants with plantar fibromatosis were assessed. The effect of EN3835 on investigator and patient-reported outcome measures were also evaluated,

The study randomized 24 participants into 3 treatment groups (8 participants per treatment group). On Day 1, participants were randomized in a 1:1:1 ratio to 3 treatment concentrations of EN3835. Based on the maximum diameter of the nodule collected on ultrasound, participants received either 1 (for nodules ≤ 1.5 cm) or 2 (for nodules > 1.5 cm) injections of EN3835 per nodule. The total dose per nodule ranged from 0.12 to 0.45 mg for nodules ≤ 1.5 cm and 0.24 to 0.9 mg for nodules > 1.5 cm. Blood samples were drawn for PK analysis on Day 1 before dosing and at 10, 20, 30, 60 minutes and 2, 4, 8, 12, and 24 hours following injection.

During the Initial Treatment Period, participants returned to the clinic for 4 follow-up visits, 1 week apart, on Days 8, 15, 22, and 29. On each visit day, the nodules were palpated, caliper measurements of the treated nodules were collected, and an ultrasound was conducted. At each visit, the participants completed the Foot Function Index-Short Form-23 (FFI-SF-23) and the Participant Satisfaction with Treatment Scale. In addition, the Investigator Assessment of

Improvement with Treatment Scale was completed at each visit. Safety was assessed by the incidence, severity, and duration of treatment-emergent adverse events (TEAEs). Nodule size was assessed from baseline to the end of study (EOS) visit (Day 57 \pm 5 days).

A Retreatment Period was added to the EN3835-105 study to allow for retreatment of treated nodules and to assess the safety, tolerability, and efficacy of multiple doses of EN3835 in the treatment of plantar fibromatosis. Based on the result of an interim analysis, the concentration and dose of EN3835 selected for use in the Retreatment Period, was EN3835 2.25 mg/mL ranging from 0.45 mg (for nodules \leq 2 cm) to 0.9 mg per nodule (for nodules $>$ 2 cm) .

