After the Initial Treatment Period, almost all (90%) nodules improved by at least 1-level in nodular consistency in the EN3835 2.25 mg/mL and 1.2 mg/mL treatment groups, and in the EN3835 0.6 mg/mL treatment group, 72.7% of nodules had at least a 1-level improvement. All (100%) participants in the EN3835 2.25 mg/mL and almost all (87.5%) participants in the 1.2 mg/mL treatment groups had at least a 1-level improvement in nodular consistency. There was an overall improvement in the FFI-SF-23 composite score in the EN3835 of -48.7%, with a negative change representing an improvement. On a nodular level, 73.3% of nodules improved by at least 1-level in nodular consistency. There was an incremental improvement of -9.3% in the FFI-SF-23 mean (SD) composite score by Day 57. On a nodular level, in all treatment groups, \geq 72.7% of nodules were responders on the Subject Satisfaction with Treatment Scale. On a participant level, in all treatment groups \geq 75% of participants were responders on the Subject Satisfaction with Treatment Rating Scale and the Investigator Assessment of Improvement Scale. There were small and inconsistent changes in nodule size (with increases and decreases) as measured by calipers, However, ultrasound measurements remained relatively unchanged and therefore did not correlate with other measures of improvement. There was no quantifiable systemic exposure of AUX-II following intralesional EN3835 injection of up to 2 injections of 0.9 mg in the foot and up to 1.8 mg per total dose

During the Retreatment Period, by Day 57, after administration of 1 or 2 treatments of EN3835 2.25 mg/mL, almost all participants (81.8%) had nodules that improved by at least 1 level in consistency. Additionally, 63.6% of participants were responders on the Subject Satisfaction with Treatment Rating Scale. On a nodular level, on, 66.7% of nodules were responders on the Subject Satisfaction with Treatment Rating Scale.

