3.2.2. EN3835-106

Study EN3835-106 is a Phase 1, open-label study to assess the safety, tolerability, and PK of EN3835, administered intralesionally at total doses of either 1.8 mg, 2.7 mg, or 3.6 mg in participants with complex configurations of their plantar fibromatosis nodules. The effect of EN3835 on foot function, nodule hardness, nodule consistency, and nodule size will also be

assessed. To be eligible for treatment participants must have unilateral or bilateral palpable hard or firm plantar fibromatosis nodules with a nodule configuration requiring 4 (1.8 mg), 6 (2.7 mg) or 8 (3.6 mg) injections of EN3835. Based on the total count, distribution, and size of the nodules to be treated, participants will be allocated into a low dose (1.8 mg total dose), medium dose (2.7 mg total dose), or high dose (3.6 mg total dose) cohort.

Depending on the size of the nodule, each nodule will be treated with intralesional EN3835 0.45 mg (for nodules ≤ 2 cm), 0.9 mg (for nodules $> 2 - \leq 4$ cm), 1.35 mg (for nodules $> 4 - \leq 6$ cm), or 1.8 mg (for nodules > 6 cm). PK and immunogenicity samples will be collected throughout the study.

After the first dose of EN3835, participants will return for a total of 8 outpatient follow-up visits, on Days 2 (24 hours after injection), 3 (48 hours after injection), 8 (168 hours after injection) and 22 (504 hours after injection) for collection of PK samples (collected within 10% of nominal time point). Biweekly on Days 15, 29, 43, and 57 nodules will be measured using calipers, nodule hardness will be assessed via a durometer, nodular consistency by palpation, participant assessments of foot function (pain, difficulty, and activity limitation) and treatment satisfaction, and clinician assessments of improvement. Treated feet will be photographed through Day 22 to document bruising, ecchymosis, and any other similarly related visible local reactions post injection.

Participants will complete the study on Day 57 (EOS Visit) during which immunogenicity samples will be collected, safety will be assessed and the nodules will be measured. The maximum duration of study participation is up to 85 days (Screening Period: 28 days, Dosing Period: 1 day, and a total Follow-up Period of 56 days).

To date, the study is on hold.

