3.3.3. Overall Assessment of Benefit and Risks

The assessment of the likelihood of these AEs occurring in participants with plantar fibromatosis was evaluated while taking into consideration the range of doses of EN3835 to be administered in this study. Based on the overall benefit-risk assessment and the precautions taken into account in this protocol, it is concluded that EN3835 administered as doses ranging from 0.45 mg to 1.35 mg per nodule per foot (for participants with unilateral plantar fibromatosis) for up to 2 treatment visits with a maximum total dose of 1.8 mg per treatment visit (for participants with bilateral plantar fibromatosis) has an acceptable benefit-risk ratio.

Strict inclusion and exclusion criteria, safety monitoring, and clinician training on injection technique will ensure appropriate use of EN3835. In summary, the potential risks to participants with plantar fibromatosis in this study are outweighed by the potential benefits that may result from the clinical development of EN3835 for patients with symptomatic nodules due to plantar fibromatosis.

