7.1. Selection of Nodules

During the Screening and Day 1 Visits, the investigator will examine and evaluate the nodules on the affected foot/feet, by conducting caliper measurements, measuring nodule hardness using a durometer, palpating the nodule for consistency, and assessing the FFI. Only hard, firm throughout, moderately firm fibrous nodules that are palpable on clinical examination and measurable on calipers are eligible for treatment on Day 1. All hard, firm throughout, moderately firm nodules present on each foot on Day 1 must be treated. (If all nodules on each foot are not hard, moderately firm or firm throughout on Screening and Day 1, the participant will not be eligible for study inclusion). Study intervention will be administered intralesionally to nodules present meeting eligibility criteria based on the size of each nodule at the doses described in [Table 2](#).

Based on the largest diameter of width or length of the nodule determined by calipers, participants will receive 1 to 3 injections of study intervention per foot. Participants with nodules of ≤ 2 cm will receive 1 intralesional injection of study intervention per nodule. Participants with nodules of > 2 cm to ≤ 4 cm will receive 2 intralesional injections of study intervention per nodule. Participants with nodules of > 4 cm will receive 3 intralesional injections of study intervention per nodule.

Nodules treated on Day 1 that remain palpable on Day 29 clinical examination and have consistency of hard, firm throughout, moderately firm, or soft are eligible for a second treatment on Day 29.

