7.3. Study Intervention Administration

Details of the study intervention and administration are presented in Table 1. Specific instructions for EN3835/placebo reconstitution and preparation of administration syringes will be provided in the Pharmacy Manual. Study intervention will be injected intralesionally. Specific instructions outlining the injection techniques will be provided in the Study Operations Manual.

Table 1: Study Intervention Administration

Treatment Concentrations	EN3835	Placebo
Product Name	EN3835 (0.9 mg of collagenase clostridium histolyticum with 0.5 mg of hydrochloric acid, 18.5 mg of sucrose and 1.1 mg of tromethamine) plus diluent	Placebo (0.5 mg of hydrochloric acid, 18.5 mg of sucrose and 1.1 mg of tromethamine) plus diluent
Type	Biologic	NA
Dose Formulation	Injectable liquid	Injectable liquid
Unit Dose Strengths	2.25 mg/mL	NA
Dose Amount and Frequency ^a	0.45 mg administered as 1 injection 0.9 mg administered as 2 injections 1.35 mg administered as 3 injections	Volume matched placebo administered as 1 injection, 2 injections, or 3 injections per nodule depending on nodule size
Route of Administration	Intralesional injection	Intralesional injection
Sourcing	Provided centrally by the sponsor	Provided centrally by the sponsor
Packaging and Labeling	Product will be provided in vials. Each vial will be labeled per country requirement.	Product will be provided in vials. Each vial will be labeled per country requirement.

^aEach injection (0.45 mg) of study intervention will be administered as 2 aliquots of 0.225 mg each.

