6.4. Subgroup Analyses

Exploratory subgroup analyses will be performed on the primary endpoint, key secondary endpoints, and frequency of TEAE. The subgroups are:

1. Number of injections (1 vs 2 vs 3 vs 4) at Day 1
2. Baseline FFI Total Pain Subscale Score: Group 1 vs Group 2
 - a. Group 1: FFI total pain subscale score ≤ 20 for participants without orthotics or FFI total pain subscale score ≤ 26 for participants with orthotics
 - b. Group 2: FFI total pain subscale score ≥ 21 for participants without orthotics or FFI total pain subscale score ≥ 27 for participants with orthotics

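### By the protocol's own account EN3835-105 gave at most 0.9 mg per nodule per treatment; Table 2 gives 1.35 mg to a nodule over 4 cm, the dose justification does not address this, and no safety table in the SAP separates that exposure

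*Protocol*

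**What the plan says.** **Dose in this study.** Doses are assigned nodule by nodule from the caliper size. Protocol 7.1 states: "Participants with nodules of > 4 cm will receive 3 intralesional injections of study intervention per nodule". Table 1 gives the amount: "1.35 mg administered as 3 injections". Table 2 lists the same dose, in 0.6 mL, in its last row. SAP 3.3 and SAP Table 4 repeat the scheme. Protocol 3.3.3 finds an acceptable benefit-risk ratio for "EN3835 administered as doses ranging from 0.45 mg to 1.35 mg per nodule per foot" in unilateral disease.

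**Stated justification.** Protocol 5.2.2 sets the maxima at 1.8 mg when both feet are treated and 1.35 mg when one foot is treated, "given that these were the maximum doses evaluated in Study EN3835-105".

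**What the protocol reports of EN3835-105.** For the Initial Treatment Period, 3.2.1 says: "The total dose per nodule ranged from 0.12 to 0.45 mg for nodules" of 1.5 cm or less, and 0.24 to 0.9 mg for larger ones. For the Retreatment Period the range is 0.45 to 0.9 mg per nodule. Section 5.2.2 confirms one or two injections per nodule in the initial phase. On exposure per foot, 3.2.1 has only this clause, in a sentence about systemic exposure: "up to 2 injections of 0.9 mg in the foot and up to 1.8 mg per total dose".

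**Other plantar data.** EN3835-106 also lists 1.35 mg (and 1.8 mg) for a single nodule, but "To date, the study is on hold", and no results are cited.

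**Safety analysis.** The dose-related subgroup for treatment-emergent adverse events is "Number of injections (1 vs 2 vs 3 vs 4) at Day 1" (SAP 6.4, repeated in 7.6.5). Groups with fewer than 10 participants may be merged with adjacent ones. SAP 7.7.1 summarises exposure by number of injections and by one or both feet. The adverse event tables in SAP 7.7.2 carry no dose dimension.

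**The concern.** The unit of dosing is the nodule, but the statement that links the maxima to experience in this disease is in other units. A reader of 5.2.2 would take the highest doses here to have been given before. Per nodule, the protocol's own figures do not show that.

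The harms at issue are local. Section 3.3.2 warns of serious local injury, and plantar fascial tear is an adverse event of special interest. If such events cluster in nodules that received three injections, the planned subgroup would mix them with participants whose three injections were spread over several small nodules or over two feet. The tables would then be least informative at the per-nodule dose for which the protocol reports no prior plantar data.

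**Working it through.** **1. Reproduce Table 2.** Dose = volume × 2.25 mg/mL: 0.2 mL gives 0.45 mg, 0.4 mL gives 0.90 mg, 0.6 mL gives 1.35 mg. Injections × 0.45 mg gives the same three values. Table 2 is internally correct.

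**2. Reproduce the EN3835-105 range.** Implied volume = dose / concentration.
- Lowest concentration, 0.6 mg/mL: 0.12 / 0.6 = 0.2 mL and 0.24 / 0.6 = 0.4 mL.
- Highest concentration, 2.25 mg/mL: 0.45 / 2.25 = 0.2 mL and 0.9 / 2.25 = 0.4 mL.

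So 0.12 to 0.45 mg is one injection and 0.24 to 0.9 mg is two. The maximum per nodule per treatment is two injections, 0.4 mL, 0.9 mg.

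**3. Compare per nodule.** 1.35 / 0.9 = 1.5 (three injections against two; 0.6 mL against 0.4 mL).

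**4. Compare per foot.** The clause in 3.2.1 has two readings. Two injections totalling 0.9 mg give 0.9 mg in the foot. Two injections of 0.9 mg each give 2 × 0.9 = 1.8 mg in the foot. The first fits 0.45 mg per injection; the second does not. Neither equals the 1.35 mg that 5.2.2 calls a maximum evaluated. A foot with one 0.9 mg and one 0.45 mg nodule would give 1.35 mg and would be consistent with 3.2.1, but the protocol does not say that this occurred.

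**5. What the three-injection subgroup contains.** Inclusion 4 and exclusions 4 to 6 allow these configurations with three injections at Day 1:

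| Disease | Nodules | Highest dose in any one nodule |
|---|---|---|
| Unilateral | one > 4 cm | 1.35 mg |
| Unilateral | one > 2 to 4 cm and one ≤ 2 cm | 0.90 mg |
| Unilateral | three ≤ 2 cm | 0.45 mg |
| Bilateral | one > 2 to 4 cm; one ≤ 2 cm in the other foot | 0.90 mg |
| Bilateral | one ≤ 2 cm; two ≤ 2 cm in the other foot | 0.45 mg |

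One of five carries 1.35 mg in a nodule. Restricting to one treated foot still leaves three configurations. The one-, two- and four-injection groups contain no 1.35 mg nodule, because bilateral participants with a nodule over 4 cm are excluded and unilateral participants are capped at three injections. Merging a small three-injection group with a neighbour could therefore only dilute it.

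**6. Likely size of the cell.** The documents do not give the share of participants with a nodule over 4 cm. Assumed shares of the 86 EN3835 participants, with the one-sided 95% upper limit for an event rate when no event is seen, 1 − 0.05^(1/n):

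| Assumed share | n | Upper limit, zero events |
|---|---|---|
| 2% | 2 | 78% |
| 5% | 4 | 53% |
| 10% | 9 | 28% |
| 15% | 13 | 21% |

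**The case against.** Much of the case on the other side stands, and it limits the point.

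- **A reader might infer that 5.2.2 is false.** It makes no per-nodule claim, so the per-nodule figures do not contradict it. They show that it does not cover the unit in which the trial doses.
- **A reader might infer that 1.35 mg was never given to one foot in EN3835-105.** The clause in 3.2.1 is unclear, and a foot with mixed nodule sizes could have received it. The figure is untraceable, not disproved.
- **A reader might infer a higher local concentration of drug.** In EN3835-105 any nodule over 1.5 cm received two injections in the initial phase, whereas 1.35 mg is reserved here for nodules over 4 cm. As an illustration, (4 / 1.6)² = 6.25 times the area for 1.5 times the dose, although the earlier study sized nodules by ultrasound and this one uses calipers. The finding concerns absolute dose per nodule only.
- **A reader might see two treatments, 2 × 1.35 = 2.7 mg, as new cumulative exposure.** EN3835-105 retreated nodules already treated, with one or two further treatments, so 0.9 + 2 × 0.9 = 2.7 mg was possible there, over a longer time. Novelty is not shown.
- **A reader might conclude that the trial cannot report local toxicity.** It can. The SAP plans tables of special-interest and severity-graded events, participant listings, and a baseline nodule-size category over 4 cm. An unblinded safety board also reviews the data. What is missing is the cross-tabulation.
- **A reader might fault the Day 1 restriction.** It is sound. Treatment 2 depends on residual nodules and investigator judgement, so counting Day 29 injections would group participants by a post-randomisation decision.
- **A reader might take the hold on EN3835-106 as a safety signal.** No reason is given, so nothing follows beyond the absence of results.

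It is also fair that 3.3.3 draws on experience in other indications and on mitigation measures, not on EN3835-105 alone. That does not supply a per-nodule figure for plantar nodules.

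**Conclusion.** The point holds in a limited form. Per nodule and per treatment, this study's highest dose is 1.5 times the highest that the protocol describes for the study it cites. The justification sentence does not address this, and its per-foot figure cannot be recovered from the background section. The planned safety subgroup mixes the 1.35 mg nodule with four other configurations whose highest per-nodule dose is 0.45 or 0.9 mg.

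This rests on the protocol's summary of EN3835-105, since that study's report is not available here, and on the tables described in the SAP text, since the table shells and the safety board charter are separate documents. The primary analysis and sample size are unaffected. The sponsor should correct it because the prior-exposure statement underpins the dose cap and the missing table concerns local safety.

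**What to change.** **Protocol.** Reconcile 3.2.1, 3.3.3, 5.2.2 and Table 2. State the maximum dose per nodule and per foot actually given in EN3835-105, resolve the ambiguous per-foot clause, and say plainly where this study exceeds those figures. Which dose is right is for the sponsor; none is proposed here.

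**SAP 7.6.5 and 7.7.2.** Add one descriptive table of treatment-emergent events, events of special interest and Grade 3 or higher local events, by treatment group and by the highest number of injections given to any one nodule at Day 1 (1, 2 or 3). Placebo is volume-matched, so the same rows apply to both arms. Exempt the three-injection row from the rule on merging small groups. If a version including Day 29 injections is wanted, label it descriptive only.

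**Cost.** Wording in a few protocol sections and one table from nodule sizes and injections already recorded. Eligibility, dosing and efficacy analyses do not change. The price is a less favourable statement of prior exposure and a small, imprecise row: on the assumed shares, about 2 to 13 EN3835 participants.
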